## 4.0 Eligibility

We plan to enroll 120 adult (age 21 and over) conventional cigarette smokers from the Chicago metro area to participate in this study. The eligibility criteria will be assessed via an online screening survey, a follow-up screening phone call with project staff, and an in-person assessment prior to enrollment. Recruitment materials will direct potential participants to a website to complete an online survey to determine initial eligibility. Following this initial screening, we will call potential participants to describe the study requirements, re-assess key eligibility criteria, and schedule the enrollment/baseline visit for those who remain interested. Finally, at the enrollment/ baseline visit, participants must have an expired CO level of 3 ppm or greater and a negative pregnancy test (for female participants of childbearing age, 55 years old or younger) to proceed with enrollment into the study.

Study staff will review responses to the online screening surveys and conduct the phone follow-up calls as well as administer the expired CO test and record the result from the urine pregnancy test (where applicable) to determine eligibility. All screening data will be recorded in a REDCap database and will be reviewed and approved by Co-I, [name].

## 5.0 Inclusion Criteria

Inclusion criteria are: 1) men and women 21 years of age or older; 2) daily smoking rate of 3 cigarettes/day or greater for at least one year; 3) interested in reducing cigarette use; 4) willing to try e-cigarettes; 5) able to attend in-person assessments at our research office over a 14 week time period; 6) able to read and speak English; 7) agree to use an approved form of birth control during the study (if female and of childbearing age); 8) agree to refrain from using any other vaping or e-cigarette products and devices for the 12-week treatment period; 9) agree to not modify the SREC device and pods in any way; and 10) an expired CO level of 3 ppm or greater (assessed in-person at the enrollment/ baseline visit). A prospective participant's ability to speak English will be assessed directly via the online screening survey as well as their ability to communicate during the telephone screening call, and the ability to read English will be assessed indirectly by comparing responses to the online screener and telephone screener and will be verified during the informed consent process.

## 4.2 Exclusion Criteria

Exclusion criteria are: 1) current use of any smoking cessation medication or participation in a smoking cessation program or study; 2) current daily ENDS user; 3) currently breast feeding, pregnant, or trying to get pregnant (if female); 4) known allergy to propylene glycol or vegetable glycerin; 5) diagnosed with previous or current EVALI; 6) uncontrolled hypertension and/or, severe mental health problems; 7) current respiratory health conditions (e.g., asthma, COPD); and 8) no two members of the same household may participate in this study. Potential participants who respond inconsistently to the same questions on their cigarette and e-

cigarette use during the screening process will also be excluded. Individuals who are unable/unwilling to carry and interact with the EMA device during two weeks of their first month in the study will also be excluded.

## 5.0 Subject Enrollment

**UIC Recruitment.** We will inform potential participants about the research study via study flyers posted in a variety of locations in the Chicago area (e.g., coffee shops, laundromats, convenience stores); Chicago-based newspapers (including alternative newspapers or entertainment publications such as the Chicago Reader and the RedEye Chicago); social media (e.g., Facebook, Twitter, or Google ads); and an email shared via an electronic listserv to the broader UIC community (which includes all faculty, students, and staff). In addition, we may recruit smokers through research registries (UI Health Research Registry, The New Normal), and the extensive University of Illinois (UI) Health network and clinics via flyers posted in waiting areas and placed on reception area/sign-in counters.

All recruitment materials will direct potential participants to a website to complete a web-based screening survey in REDCap. The materials also include the study phone number so that potential participants can speak to a study staff member if they have questions about the research study prior to completing the online survey. Study staff will review responses to the online screening survey in order to determine initial eligibility. Following this initial web-based screening, study staff will call the potential participants who are eligible based on their initial responses and describe the study requirements in greater detail, re-assess key eligibility criteria, and schedule the enrollment/baseline visit for those who remain eligible and interested. The final eligibility assessment occurs during the enrollment study visit where potential participants complete an expired CO assessment and complete a pregnancy test (if female). If eligible after these processes, they begin the consent process with study staff.

Potential participants who are not eligible at screening are informed by email (after the online survey and/or phone screening survey), phone call, or in-person (after the CO assessment and pregnancy test) based on where in the screening process they were excluded. The responses ineligible individuals provided to the screening questions will be maintained as part of the dataset in order to accurately report recruitment and enrollment summaries; however, all identifiable information (e.g., names, phone number, email address, etc.) provided by ineligible individuals will be deleted from all study records at the end of the 1-year recruitment period. The data that remains will only be associated with a study ID. We plan to maintain the contact information during the recruitment period in order to mark ineligible individuals who complete multiple online screening surveys in an effort to enroll in the study despite an initial determination that they were ineligible.

We ensure that our recruitment methods minimize coercion in several ways. First, throughout the screening process potential participants are repeatedly informed that the decision whether or not to participate in the study is entirely their own. We provide detailed study information at all three screening points (online, phone, and during the consent process) to ensure potential participants have a full and complete understanding of what participation in the study involves and let them know that no one will be upset if they decide not to participate in the study. During the consent process we also provide participants with other alternate treatment options for reducing their smoking or helping them to quit, including several other no-cost options (e.g., Illinois Tobacco Quit Line, American Lung Association's online stop smoking link). For our recruitment in UI health clinics, UI clinical staff are not involved in the study in any way. The only involvement is that flyers and handouts about the research study will be available in the clinics. UI Health patient participation in any part of the study (screening through follow-up) is not part of their medical record. We will never share with UI Health clinic staff whether or not their patients completed a screening survey, if they were eligible, or if they enrolled in the study. None of the research staff involved in this study have clinical responsibilities at UI Health.

**Trialfacts Recruitment.** Trialfacts is a research study recruitment service to which the general population can voluntarily subscribe to receive email notifications about research participation opportunities. When individuals subscribe, they agree to be contacted for future research study opportunities. This study will be listed on the Trialfacts website so that individuals can search studies to identify those for which they may be interested or eligible (similar to the UI Health Research Registry). Trialfacts will also post approved recruitment content on social media. Potential participants who are recruited through Trialfacts will complete the web-based screening survey with Trialfacts. Trialfacts will share the online screening responses of the potentially eligible

respondents with UIC study staff via UIC's installation of REDCap. Once the data is shared, the remaining screening, eligibility, and enrollment process are the same as described above.

## 6.0 Study Design and Procedures

All human subjects research will be conducted at the Institute for Health Research and Policy at UIC. Some portions of the data analyses conducted by Co-I [name] may take place at the University of Chicago. [name] role involves guiding the data analyses and writing up results for presentation and publication. [name] will only have access to a deidentified dataset and will not have any responsibility for recruitment, enrollment, consent, or data collection, and will never be able to access any participant contact information.

**Design Overview.** Participants will complete baseline assessments and a one-week EMA wave while they continue their usual pattern of cigarette use. After their first EMA week, participants will be randomized (within sex) in a 1:1 ratio to receive either SREC pods in their usual flavor (n=60) or pods in their choice of flavor (n=60). Participants assigned to the flavor choice condition can select from the four available SREC flavors (tobacco, menthol, watermelon, and blueberry) based on their preference and satisfaction with the flavor throughout the trial. All participants will receive brief behavioral counseling about reducing their cigarette use and switching to the SREC. After an initial week of using SREC and reducing the number of cigarettes smoked, participants will complete another EMA week assessing patterns and responses to use of both products. Participants will receive 12 weeks of SREC pods; complete daily reports of product use along with bi-weekly check-ins through the end of the 12-week trial, and then complete a one-month follow-up. Female participants of childbearing age (55 years old and younger) will provide urine for a required pregnancy test every 5 to 6 weeks and will be removed from the study if the test indicates a pregnancy. The total study duration for participants is 18 weeks. Table 1 shows the timeline of assessments, procedures, and modality.

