**AIM 1: Examine whether conventional cigarette smokers can significantly reduce their combustible cigarette use by switching to SREC.** We hypothesize that smokers randomized to the flavor choice condition will show significantly greater reductions in combustible cigarette use than smokers in the usual flavor condition. We will assess changes in use of products over a 12-week trial. We will also examine moderators of effects, including sex, baseline menthol cigarette use (not SREC flavor), and nicotine dependence level at baseline.

**AIM 2: Examine whether reductions in conventional cigarette use and uptake of SREC are associated with changes in health and biomarker variables.** We will have longitudinal measures of all

combustible tobacco products as well as SREC use and will examine how these longitudinal changes in patterns of use are associated with changes in expired air carbon monoxide (CO); blood pressure; heart rate; weight; respiratory symptoms; withdrawal symptoms; and nicotine dependence. We hypothesize that smokers who show more complete substitution will show greater reductions in CO and respiratory symptoms.

**AIM 3: Examine smokers' subjective responses to SREC in real time, as they are used, and whether these responses are associated with cigarette reduction.** We hypothesize that smokers in the flavor choice condition will show more adherence to the switching intervention and report higher levels of satisfaction, pleasure, and mood enhancements than smokers in the usual flavor EC condition and that these responses will predict level of cigarette reduction. Data will come from EMA measures and daily surveys. We will also descriptively examine how SREC flavor may be associated with subjective responses.

**AIM 4: Examine how patterns of use (e.g., contexts, timing) and subjective experience with SREC differ from conventional cigarette use, and whether differences are associated with success in switching to SREC.** These within-subject analyses will use EMA data. We hypothesize that subjects who have fewer differences in patterns and experiences between cigarettes and SREC will reduce cigarettes more and maintain SREC use longer.

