**Baseline/Enrollment Visit Week 1.** The first visit begins with the final set of screening assessments: CO > 3ppm and negative pregnancy test for female participants. Once the screening is complete, participants who remain eligible will start the consent process. Staff describe the study, answer all questions, ensure understanding of the study information, and re-assess interest in participating. Participants who remain interested will be asked to sign the informed consent form. Participants will complete the baseline questionnaire on a tablet, and participants will have vital signs taken (blood pressure, heart rate, height, weight). Participants will also be trained on the EMA protocol (see below for more details) and given instructions to go home and smoke as they usually do. **The purpose of this first EMA week is to provide baseline data about the participant's smoking pattern which will be compared to their SREC/cigarette use pattern after switching.**

**Week 2 Visit.** Participants will complete a brief questionnaire and complete an expired CO assessment. Study staff conduct a debriefing interview to review the EMA week and their compliance with the protocol. Participants will be randomly assigned to the two flavor conditions, stratifying for gender. Those participants assigned to the choice condition will select from four SREC flavors (tobacco, menthol, watermelon, and blueberry) based on their preference. Participants assigned to the usual flavor condition will receive tobacco pods if they smoke regular cigarettes and menthol pods if they smoke menthol cigarettes. Participants in both conditions will receive **brief behavioral counseling** (see below for more details) on reducing their combustible cigarette use and using SREC as a substitution for cigarettes. Starting this week, participants begin to receive daily email or text prompts (based on participant's preferred mode of communication) to complete a brief online survey on their use of cigarettes, SREC, and non-SREC e-cigarette use each day.

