## 9.0 Data Analysis

**Aim 1. Examine whether conventional cigarette smokers can significantly reduce their combustible cigarette use by switching to SREC.** We will have assessments of the amount of SREC and combustible cigarettes used every week for 12 weeks. SREC/e-cigarette use per day is captured by the total number of e-cigarette episodes defined as about 15 puffs or a period lasting about 10 minutes. Both of these outcomes will be modeled as count data (average # cigs/day and SREC episodes/day for each week) using a mixed-effects Poisson regression model (or Negative Binomial model if the Poisson assumption of equality of mean and variance is not met). In these analyses, we will examine primarily linear and curvilinear changes across time using orthogonal polynomial transforms, in order to assess the independent effects of these two types of trends, which will be treated as random effects to allow heterogeneity across subjects in the time trends. These time trend analyses will allow us to investigate the **sustainability of reductions in cigarette use and changes in SREC use**. In addition to the effect(s) of time, the main independent variable is group (usual flavor or flavor choice). Although we expect the group effect to be consistent across the 12 weeks, we will test whether the group effect varies across time (i.e., group by time interaction). For example, it may be likely that differences between the groups increase over time if the usual flavor group more rapidly relapses back to smoking cigarettes and gives up on their SREC. Our primary endpoint will be the model-based estimate of the group difference at the final 12-week timepoint (study week 14). We will also consider the proportion of participants who achieve total abstinence from combustible cigarettes at the end of the 12-week trial (defined as no cigarette smoking in the past 7 days and confirmed by CO < 3 ppm; see power section). Although our primary endpoint is the end of the 12 weeks of treatment, (week 14) we will also evaluate effects at the one-month follow-up. In terms of these primary outcomes, we will further examine the degree to which

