group differences are moderated by gender, baseline menthol cigarette use (not SREC flavor), and nicotine dependence level, and also examine the degree to which baseline characteristics might predict success on these outcomes. We will use descriptive statistics to report the frequency of flavor choice, how that varies over time, by condition, and by level of reduction.

We will also be weighing all returned SREC pods and will also be able to develop a measure of SREC use per week based on SREC pod weight.

**Aim 2. Examine whether reductions in conventional cigarette use and uptake of SREC are associated with changes in health and biomarker variables.** Smokers may vary in how completely they substitute SREC for their conventional cigarettes. Thus, for each participant, we will have, on a weekly basis, the number of cigarettes smoked and the number of SREC episodes or returned SREC pod weights. As indicated above, these will be modeled using mixed models for counts, which yield empirical Bayes estimates for each subject of their change across time in cigarette and SREC usage. We will examine how these change in usage estimates are associated with changes in the following variables: 1) CO level; 2) blood pressure; 3) heart rate; 4) weight (assessed baseline and at end); 5) self-report of respiratory symptoms (baseline and at end); and 6) nicotine dependence (assessed at baseline and end). For each of these continuous outcomes, we will use linear mixed models with effects of time and group (usual flavor or free choice), and group by time interaction if significant. To these models, we will add in the empirical Bayes estimates of cigarette and SREC change (obtained from the stage 1 mixed models for counts) and specifically examine the change by time interactions (and change by group by time if the group by time interaction is significant). As the empirical Bayes estimates from the stage 1 analyses have uncertainty attached to them, we will use the resampling approach advocated by Tsonka et al for using empirical Bayes estimates from a first stage analysis as covariates in a second stage model.

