**Aim 4. Examine how patterns of use (e.g., contexts, timing) and subjective experience with SREC, differ from conventional cigarette use, and whether differences are associated with success in switching to SREC (giving up or reducing combustible and using SREC).** We will have baseline EMA data on smoking events and random time sampling of urges, mood, satisfaction with smoking, as well as context. Then we will have a week of EMA data on the second week of the instructed switch to SREC. We will compare EMA data during baseline to the SREC switch week on the following within subject factors: context of use (alone, with others; location – home; work; in public; presence of other smokers; time of day (e.g., first cigarette of the day); mood prior to use; mood after use; urge prior to use and at random time; satisfaction after use). We will use three-level (observations within weeks within subjects) linear mixed models for continuous outcomes (mood), logistic mixed models for binary outcomes (context), and survival mixed models for time to an event (first cigarette of the day). The main independent variable will be the indicator of EMA week (baseline/switch week) to test whether the outcomes vary by EMA week. We will also control for group (usual flavor/flavor choice) and examine whether the effect of EMA week varies by group. Analyses will also include sex and prior menthol use as covariates.

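### The Aim 1 primary model adjusts for neither sex, the only stratification factor, nor baseline menthol use, which decides the pod a usual-flavor participant receives

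*Combined protocol and SAP*

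**What the plan says.** **Randomisation.** Section 6.0, Design Overview: "participants will be randomized (within sex) in a 1:1 ratio to receive either SREC pods in their usual flavor (n=60"), with 60 more in the choice arm. The Week 2 Visit paragraph repeats it: "Participants will be randomly assigned to the two flavor conditions, stratifying for gender". No section names menthol status as a stratification factor.

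**Control product.** Week 2 Visit paragraph: "Participants assigned to the usual flavor condition will receive tobacco pods if they smoke regular cigarettes and menthol pods if they smoke menthol cigarettes". The choice arm picks from all four flavors whatever the baseline cigarette type.

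**Role of menthol in the analysis.** Section 3.0, Aim 1, lists the moderators as "including sex, baseline menthol cigarette use (not SREC flavor), and nicotine dependence level at baseline", and Section 9.0 repeats that it will examine whether "group differences are moderated by gender, baseline menthol cigarette use (not SREC flavor), and nicotine dependence level". For Aim 4, Section 9.0 adds: "Analyses will also include sex and prior menthol use as covariates".

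**Aim 1 primary model.** Section 9.0: "In addition to the effect(s) of time, the main independent variable is group (usual flavor or flavor choice"), together with a test of group by time. The primary endpoint is the model-based group difference at the final 12-week timepoint (study week 14). No baseline covariate is listed for this model or for the abstinence comparison.

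**The concern.** A factor used to stratify the allocation normally belongs in the primary model. Otherwise the standard error ignores balance that the design created. Sex is missing from the Aim 1 model as written.

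Menthol use has a different claim to be there. It decides which comparison a participant is in: a menthol smoker is compared on menthol pods against free choice, a regular smoker on tobacco pods against free choice. The plan itself treats menthol use as important enough to be an Aim 1 moderator and to stand beside sex as an Aim 4 covariate. For the primary comparison, however, it is neither balanced by design nor adjusted for. If it is prognostic for cigarettes per day, a chance difference in menthol share moves the unadjusted estimate in the one trial that is run, and the unexplained variation costs some power.

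**Working it through.** **Inputs from the documents.** 60 per arm, 1:1 (Section 6.0). 10% attrition, 54 per arm at the end, power 0.8, rate ratio 0.75, abstinence 31.5% vs 10% (Section 12.0). Two-sided alpha 0.05 is stated only for Aim 4 and is assumed here.

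**Assumptions.** The documents give neither the share of menthol smokers nor its effect on smoking. I take a share of 30% to 70% and a rate ratio by menthol status of 1.25 to 1.3 (either direction). Sex strata are ignored in the imbalance calculation.

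**1. The plan's own figures.** 120 × 0.9 = 108, or 54 per arm. Power for 31.5% vs 10% with 54 per arm is 0.795 by the usual normal formula, which agrees with the stated 0.8. The power for the rate ratio of 0.75 cannot be checked, because no dispersion is given; power 0.8 implies a between-person coefficient of variation of about 0.52. In log terms, |ln 0.75| = 0.288, so the implied standard error is 0.288/2.80 = 0.103.

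**2. How large a menthol imbalance is by chance.** Hypergeometric, 120 people into two arms of 60:

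| Menthol share | SD of arm difference (points) | P(≥10 points) | P(≥15) | P(≥20) |
|---|---|---|---|---|
| 30% or 70% | 8.4 | 0.32 | 0.07 | 0.03 |
| 40% or 60% | 9.0 | 0.35 | 0.09 | 0.04 |
| 50% | 9.2 | 0.36 | 0.10 | 0.04 |

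The cut-off matters because the difference moves in steps of 2/60 = 3.3 points, and exactly 10 points (for example 33 vs 27) is attainable. Counting only differences above 10 points, the same calculation gives 0.16 to 0.20.

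**3. What an imbalance does to the unadjusted rate ratio.** Approximate shift = (ratio by menthol status) raised to the imbalance:

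- ratio 1.25: 1.25^0.10 = 1.023; 1.25^0.20 = 1.046
- ratio 1.3: 1.3^0.10 = 1.027; 1.3^0.18 = 1.048; 1.3^0.20 = 1.054

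So the shift is about 2% to 5%. On the log scale, with ratio 1.3, 10 points is 0.0262/0.288 = 9% of the planned effect and 18 points is 0.0472/0.288 = 16%.

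**4. Validity and power.** Simulation on the log scale (108 participants, 4,000 runs, menthol share 50%, SD set to give 80% power):

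| Menthol effect (log) | Stratified on menthol | Adjusted for menthol | Type I error | Power |
|---|---|---|---|---|
| 0.22 (ratio 1.25) | no | no | 0.049 | 0.79 |
| 0.22 | no | yes | 0.049 | 0.80 |
| 0.22 | yes | yes | 0.052 | 0.81 |
| 0.4 (ratio 1.49) | no | no | 0.052 | 0.80 |
| 0.4 | no | yes | 0.045 | 0.85 |
| 0.4 | yes | no | 0.036 | 0.81 |
| 0.4 | yes | yes | 0.046 | 0.85 |

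The simulation error on power is about sqrt(0.8 × 0.2/4000) = 0.006. Three things follow. The current scheme keeps its type I error. Adjustment gains about 5 points of power if the menthol effect is large and almost nothing at a ratio of 1.25. Stratifying adds nothing detectable once menthol is in the model, and without the adjustment it makes the test conservative.

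**The case against.** The strongest reply is that randomisation already deals with this. Chance imbalance is part of the standard error, and the simulated type I error under the present scheme is about 0.05. With a ratio of 1.3, menthol imbalance contributes an SD of about 0.262 × 0.091 = 0.024 to the log rate ratio, and (0.024/0.103)² is only about 5% of its variance. Nicotine dependence is also a named moderator and is also unstratified, and a trial of 120 cannot stratify on everything. All of this stands, and it keeps the point small.

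A reader might infer something stronger: that menthol imbalance changes the control itself, or confounds the arm contrast. The documents do not support that. The control is one rule for everyone, pods matching the usual cigarette; only the mix of tobacco and menthol pods follows the menthol share of the arm. A reader might also infer that the randomisation must be changed. For the primary comparison, adjustment alone recovers essentially the whole gain. The menthol-by-group test benefits little either: at a 50% share, an 18-point imbalance raises the variance of that interaction by about 3%.

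It can also be said that Section 9.0 partly covers menthol, by testing it as a moderator and by looking at baseline predictors of success. Those are further analyses, however. They do not put menthol or sex into the model that yields the primary estimate, and that is the part of the point that remains.

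**Conclusion.** The Aim 1 primary model as written omits the stratification factor and a baseline variable that the plan itself treats as important. The consequence is modest. A menthol difference of at least 10 points arises in roughly a third of randomisations. It would move the unadjusted rate ratio by about 2% to 3%, and differences near 20 points, with a chance of 3% to 4%, by about 5%. Lost power ranges from negligible to about 5 points. These sizes rest on an assumed menthol share of 30% to 70% and, for the shift, an assumed prognostic ratio of 1.25 to 1.3; the 5-point figure needs a ratio near 1.5. If menthol status is not prognostic, the shift and the loss vanish. There is no systematic bias, no inflation of type I error, and no bearing on the stated sample size.

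**What to change.** In Section 9.0, Aim 1, prespecify sex and baseline menthol cigarette use as covariates in the primary count model and in the abstinence comparison, and keep the moderator analyses as they are. For abstinence, state how the adjusted result will be reported (for instance a standardised risk difference), because an adjusted odds ratio is not the same quantity as a comparison of two proportions. At the planned rates about 54 × 0.10 + 54 × 0.315 = 22 abstainers are expected, so two extra binary covariates are affordable but more would not be.

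The cost is a few sentences. No new data are needed: smoking history is collected at week 1 (Section 6.3, Table 2), and menthol status has to be known at week 2 to dispense usual-flavor pods.

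Optionally, if enrolment has not begun, randomise within sex-by-menthol strata. The average of 120/4 = 30 per stratum hides unequal cells: at a 30% menthol share the two menthol strata average 120 × 0.30/2 = 18. Small blocks at a single site where staff know the arm make allocations easier to guess, so block sizes would need care. Any such stratification must come with the adjustment above.
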